8.4. Deaths

If any patient dies during the study all relevant information will be discussed in the patient’s narratives included in the CSR.

8.5. Clinical Laboratory Tests

Laboratory test results will be presented in standard international (SI) units.

Summary statistics for chemistry, hematology, urinalysis, and coagulation laboratory tests will be presented at baseline, month 1, month 3, month 4, and end of treatment visit. Laboratory values and changes from baseline to each visit and last on study assessment will be summarized using descriptive statistics. Listings of all individual patients’ laboratory tests will be presented.

Shifts (below, within, and above the normal range) from baseline to each visit and last on study assessment will be summarized using patient counts.

Summaries of potentially clinically significant abnormal values will include all postbaseline values (including scheduled, unscheduled, and early termination visits). The incidence of potentially clinically significant abnormal values will be summarized for laboratory variables using descriptive statistics with the criteria specified in [Table 3](#).

Listings of patients who have potentially clinically significant abnormal laboratory data will be presented.

Table 3: Criteria for Potentially Clinically Significant Laboratory Values

Test	Criterion value
Serum chemistry	
ALT	≥3x ULN
AST	≥3x ULN
ALP	≥3x ULN
GGT	≥3x ULN
LDH	≥3x ULN
BUN	≥10.71 mmol/L
Creatinine	≥177 µmol/L

Table 3: Criteria for Potentially Clinically Significant Laboratory Values (Continued)

Test	Criterion value	
Uric acid	Men	$\geq 625 \mu\text{mol/L}$
	Women	$\geq 506 \mu\text{mol/L}$
Bilirubin (total)		$\geq 34.2 \mu\text{mol/L}$
Hematology		
Hematocrit	Men	$< 0.37 \text{ L/L}$
	Women	$< 0.32 \text{ L/L}$
Hemoglobin	Men	$\leq 115 \text{ g/L}$
	Women	$\leq 95 \text{ g/L}$
WBC counts		$\leq 3 \times 10^9/\text{L}$ $\geq 20 \times 10^9/\text{L}$
Eosinophils		$\geq 10\%$
ANC		$\leq 1 \times 10^9/\text{L}$
Platelet counts		$\leq 75 \times 10^9/\text{L}$ $\geq 700 \times 10^9/\text{L}$
Urinalysis		
HGB		≥ 2 unit increase from baseline
Glucose		≥ 2 unit increase from baseline
Ketones		≥ 2 unit increase from baseline
Total protein		≥ 2 unit increase from baseline
Coagulation		
INR		> 1.5

ALP=alkaline phosphatase; ALT=alanine aminotransferase; ANC=absolute neutrophil count AST=aspartate aminotransferase; BUN=blood urea nitrogen; GGT=gamma-glutamyl transpeptidase; HGB=hemoglobin; INR=international normalized ratio; LDH=lactate dehydrogenase; ULN=upper limit of normal range; WBC=white blood cell.

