- j. History of clinically significant cardiovascular disease or vascular ischemia (such as myocardial, neurological [e.g., cerebral ischemia], peripheral extremity ischemia, or other ischemic event) or thromboembolic events (arterial or venous thrombotic or embolic events), such as cerebrovascular accident (including transient ischemic attacks), deep vein thrombosis, or pulmonary embolism.
- k. History of human immunodeficiency virus, tuberculosis, or chronic hepatitis B or C infection.
- l. Past or current history of cancer, except for appropriately treated non-melanoma skin carcinoma in the last 5 years.
- m. Pregnant or lactating female patients or female patients who plan to become pregnant during the study.
- n. Participation in a clinical study of a new chemical entity or a prescription medicine within 2 months before screening (or 3 months in case of biologics if the half-life of the biologics is unknown) or 5 half-lives, whichever is longer, or is currently participating in another study of an IMP (or a medical device).
- o. Any prior exposure to a monoclonal antibody targeting the CGRP pathway (such as AMG 334, ALD304, LY2951742, or fremanezumab).
- p. Any finding in the baseline 12-lead ECG considered clinically significant in the judgment of the investigator.
- q. Any finding that, in the judgment of the investigator, is a clinically significant abnormality, including serum chemistry, hematology, coagulation, and urinalysis test values (abnormal tests may be repeated for confirmation).
- r. Hepatic enzymes (alanine aminotransferase, aspartate aminotransferase, and alkaline phosphatase) $>1.5 \times$ the upper limit of the normal (ULN) range after confirmation in a repeat test or suspected hepatocellular damage that fulfills criteria for Hy's law at screening.
- s. Serum creatinine $>1.5 \times$ the ULN, clinically significant proteinuria, or evidence of renal disease at screening.
- t. The patient has a history of alcohol abuse during the 2 years prior to screening.
- u. The patient has a history of drug abuse during the past 2 years or drug dependence during the past 5 years.
- v. The patient cannot participate or successfully complete the study, in the opinion of their healthcare provider or the investigator, for any of the following reasons:
 - mentally or legally incapacitated or unable to give consent for any reason

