4.2. Specification of Baseline Values

Patients will complete electronic headache diary entries daily for 28-day run-in period and enter headache information (ie, occurrence of headache, duration of headache, maximum severity of headache, and acute migraine-specific medication use) about the previous day into the electronic headache diary device.

If the run-in period is greater or less than 28 days, the baseline values for calculating the change from baseline of the monthly values of the efficacy variables will be normalized to 28 days. The baseline value for calculating change from baseline of the weekly values will be normalized to 7 days.

The efficacy baseline values during the 28-day run-in period derived from the electronic headache diary include

- total headache days of at least moderate severity
- total number of migraine days
- total number of days of use of any acute headache medication
- total headache days of any severity
- total number of headache hours of at least moderate severity
- total number of headache hours of any severity
- total number of days of use of migraine-specific acute headache medications (triptans and ergot compounds) for the group of patients who use migraine-specific acute headache medications at baseline
- total number of days with nausea or vomiting
- total number of days with photophobia and phonophobia

Other efficacy baseline values that will be measured on day 0 before the 1st study drug administration include

- disability score, as measured by the HIT-6
- disability score, as measured by the MIDAS
- quality of life, as measured by the MSQOL questionnaire
- health status, as measured by the EQ-5D-5L questionnaire
- patient depression status, as measured by the PHQ-2 and the PHQ-9

- patient work productivity and activity impairment, as measured by the WPAI questionnaire

Other baseline values will be the last values prior to the 1st dose of study drug.

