8.7. Vital Signs

Summary statistics for vital signs (pulse, systolic and diastolic blood pressure, body temperature, and respiratory rate) will be presented at baseline, each visit, and last on study assessment. Vital signs values and changes from baseline to each visit and last on study assessment will be summarized using descriptive statistics.

Summaries of potentially clinically significant abnormal values will include all postbaseline values (including scheduled, unscheduled, and early termination visits). The incidence of potentially clinically significant abnormal values will be summarized using descriptive statistics with the criteria specified in [Table 4](#).

[Table 4](#) specifies the criteria for identifying vital signs as potentially clinically significant abnormal values. Note that in order to qualify as potentially clinically significant abnormal, a value needs to meet both criteria below: ie, have a value beyond the criterion value and a change of at least the magnitude specified in the change relative to baseline column.

Table 4: Criteria for Potentially Clinically Significant Vital Signs

Vital Sign	Criterion value	Change relative to baseline
Pulse	≥120 bpm	Increase of ≥15 bpm
	≤50 bpm	Decrease of ≥15 bpm
Systolic blood pressure	≥180 mm Hg	Increase of ≥20 mm Hg
	≤90 mm Hg	Decrease of ≥20 mm Hg
Diastolic blood pressure	≥105 mm Hg	Increase of ≥15 mm Hg
	≤50 mm Hg	Decrease of ≥15 mm Hg
Respiratory rate	<10 breaths/min	
Body temperature	≥38.3°C	Change of ≥1.1°C

bpm=beats per minute

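### SAP 8.5 reports as incidence laboratory values that may already have been beyond the Table 3 limit before the first dose; a count of new crossings should be added

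*SAP*

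**What the plan says.** SAP 8.5 defines which values feed the outlier summary: "Summaries of potentially clinically significant abnormal values will include all postbaseline values (including scheduled, unscheduled, and early termination visits"). It then says that "The incidence of potentially clinically significant abnormal values will be summarized for laboratory variables using descriptive statistics with the criteria specified in" Table 3.

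Table 3 has two kinds of criterion. Nine chemistry tests, six hematology tests and INR (16 in all) have a fixed limit. Only the four urinalysis rows are relative, each asking for a two- "unit increase from baseline".

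SAP 4.2 defines the laboratory baseline: "Other baseline values will be the last values prior to the 1st dose of study drug". Under Protocol Table 2 that is normally the visit 2 sample, taken before dosing. Neither SAP 8.5 nor SAP 4.2 applies this baseline to the Table 3 count. Protocol 9.7 removes only missing observations from categorical denominators.

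For vital signs, SAP 8.7 says "a value needs to meet both criteria below": the value must "have a value beyond the criterion value and a change of at least the magnitude specified in the change relative to baseline column". The respiratory-rate row of Table 4 is the exception, with no change specified.

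SAP 8.5 also plans changes from baseline, shifts in patient counts, and listings. The shift categories are below, within and above the normal range.

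**The concern.** Incidence ordinarily means new events. Under the rule as written, a patient whose GGT, eosinophil percentage, uric acid or hematocrit was beyond the limit before the first injection, and is beyond it again afterwards, contributes a case. Such cases say nothing about the drug. Randomization makes their expected number equal across arms, so they add the same amount to both sides of a drug-placebo ratio, and in any one trial they add chance imbalance. A reader who takes the table at its label could see a smaller relative increase than the drug produced, or an imbalance that was there before dosing.

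The other planned tables do not supply the missing number. A patient who goes from just above the upper limit of normal (ULN) for GGT to more than 3 x ULN appears in the shift table as above-to-above. A patient who was over 3 x ULN throughout falls in the same cell.

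**Working it through.** **Arm size.** The documents give no figure for laboratory outliers, so the only plan figure to reproduce is the arm size (SAP 2.4). With a difference of 1.8 days, SD 6, 90% power and alpha 0.05 (taken as two-sided): n = 2 x (1.960 + 1.282)^2 x (6/1.8)^2 = 2 x 10.51 x 11.11 = 233.5, so 234, or 235 with the t correction. Allowing for 12% dropout, 235/0.88 = 267.05, so 268. The plan's 235 and 268 reproduce.

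**Model.** Let b be the share of patients beyond the limit before dosing, s the share of those still beyond it at some postbaseline value, and p the new-onset rate in the rest. The rate reported under SAP 8.5 is q = b x s + (1 - b) x p. A count of new crossings, divided by patients not beyond the limit at baseline, estimates p itself.

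**Assumptions, none from the documents.** p = 1% on placebo and 2% on drug; s = 1; b from 0 to 3%; 268 patients per arm.

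- SD of the chance difference between two arms in carried-over patients: sqrt(2 x 268 x b x (1 - b)).
- SD of the difference in all counted patients: sqrt(268 x [q0(1 - q0) + q1(1 - q1)]), where q0 is placebo and q1 is drug.

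| b | placebo q0 | drug q1 | risk ratio | difference (points) | SD, carried-over patients | SD, all counted patients |
|---|---|---|---|---|---|---|
| 0 | 1.00% | 2.00% | 2.00 | 1.00 | 0 | 2.8 |
| 1% | 1.99% | 2.98% | 1.50 | 0.99 | 2.3 | 3.6 |
| 2% | 2.98% | 3.96% | 1.33 | 0.98 | 3.2 | 4.2 |
| 3% | 3.97% | 4.94% | 1.24 | 0.97 | 3.9 | 4.8 |

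Worked row, b = 1%: q1 = 0.01 + 0.99 x 0.02 = 0.0298; q0 = 0.01 + 0.99 x 0.01 = 0.0199; ratio 1.50; difference 0.0099.

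The true excess is 268 x (0.02 - 0.01) = 2.7 patients. The new-crossing count gives a ratio of 2.00 and a difference of 1.00 point at every b.

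**Other inputs.** With new onset of 1% and 3%, the ratio falls from 3.00 to 1.99 (b = 1%) and 1.49 (b = 3%), while the difference goes from 2.00 to 1.98 and 1.94 points. If only 80% persist (s = 0.8), the ratios are 2.11 and 1.58. The pattern is the same.

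**Which tests can be affected.** Protocol 4.2 criterion r covers "Hepatic enzymes (alanine aminotransferase, aspartate aminotransferase, and alkaline phosphatase") and excludes confirmed values above 1.5 x ULN, half the Table 3 flag of 3 x ULN. Criterion s excludes creatinine above 1.5 x ULN, against a flag of 177 µmol/L. For an assumed ULN of 84 to 110 µmol/L the entry cap is 126 to 165, below the flag; the two would meet only at a ULN of 177/1.5 = 118. For these four tests b should be near zero if the entry limits are applied, although a visit 2 value can differ from one at screening up to 28 days before.

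The other 12 tests (GGT, LDH, BUN, uric acid, bilirubin, hematocrit, hemoglobin, WBC, eosinophils, ANC, platelets, INR) have no numeric limit of their own. They rest on criterion q: "Any finding that, in the judgment of the investigator, is a clinically significant abnormality".

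**A conflict in the protocol.** Appendix R describes patients with baseline ALT or AST from 2 to 3 x ULN as eligible for enrollment. Criterion r excludes values above 1.5 x ULN. The two passages must be reconciled; until they are, the near-zero b for ALT and AST is conditional.

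**The case against.** The strongest reply is that this is one descriptive count among several laboratory outputs, with no test or alpha attached. SAP 8.5 also plans changes from baseline, shifts in patient counts and listings of individual results, so a reader could trace which flagged patients were abnormal before dosing. Results judged clinically significant become adverse events (Protocol 7.4), liver events are of special interest (SAP 8.3), and Hy's law cases enter adverse event reporting (SAP 8.5.1). Patients must be in good health by laboratory tests at entry. All of this stands, and it makes the gap one of presentation rather than lost data. It does not provide a count by arm of new crossings.

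The noise argument also needs proportion. With no baseline abnormality at all, the SD of the difference in new-onset counts is sqrt(268 x (0.01 x 0.99 + 0.02 x 0.98)) = 2.8 patients, already slightly above the assumed excess of 2.7. Carry-over worsens that limit; it does not create it, and removing carry-over would not make such an excess clearly distinguishable.

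A reader might infer that the inclusive count should be replaced, on the model of Table 4. The documents do not support that. Table 4 asks for a limit plus a change, not for a baseline inside the limit, and its respiratory-rate row asks for no change. Replacing the count would also drop from the main table a patient who worsens from an abnormal baseline, for example GGT rising from 3 to 10 x ULN.

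**Conclusion.** The point holds as a minor one. For the 16 fixed-limit tests, nothing in SAP 8.5, SAP 4.2 or Protocol 9.7 separates patients who newly cross a Table 3 limit from those already beyond it, and no other planned table does so. This follows from the absence of a condition, not from an express statement.

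If anyone is abnormal at baseline and remains so, the ratio is attenuated and noise is added, while the expected difference shrinks only by the factor (1 - b). The ratios of 1.50 to 1.24 rest on assumed new-onset rates, 1% to 3% baseline prevalence and full persistence. With b = 0 the two counts agree.

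Two stronger readings are tempting. One is that the drug-placebo comparison as a whole is diluted: the absolute comparison is not, since it moves from 1.00 to 0.97 points at most in this range. The other is that this count is the patient-level analysis of a secondary safety endpoint: the endpoint in SAP Table 1 is test results at specified time points, and the shifts are also patient counts.

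**What to change.** Keep the inclusive count in SAP 8.5. For each fixed-limit test in Table 3, add a count by arm of patients who meet the criterion at any postbaseline value and did not meet it at baseline, with baseline as in SAP 4.2. The denominator should be patients not meeting the criterion at baseline who have at least one postbaseline value. A table of baseline against worst postbaseline category, cut at the Table 3 limits, would serve equally well. Either form keeps patients who were abnormal at baseline visible. The urinalysis rows need no change.

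Separately, reconcile Protocol 4.2 criterion r with Appendix R on baseline ALT and AST.

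The cost is a sentence in the SAP and one extra row or table per test, from data already collected. Denominators will differ slightly from test to test and should be printed.

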8.5.1. Laboratory Values Meeting Hy's Law Criteria

All occurrences of possible drug-induced liver injury that meet Hy's law criteria as defined in the protocol Section 7.1.5.1 will be included in adverse events reporting.

8.5.2. Other Clinical Laboratory Tests

8.5.2.1. Human Chorionic Gonadotropin Test

Serum beta-human chorionic gonadotropin (β -HCG) tests will be performed for all women of childbearing potential at screening and end of treatment/early termination visit. Urine pregnancy tests will be performed for all women of childbearing potential at baseline, months 1 through 5, and end of treatment/early termination visit. Pregnancy test results will be listed.

8.5.2.2. Follicle-Stimulating Hormone Test

Postmenopausal women will have a follicle-stimulating hormone (FSH) test at screening. Results will be listed.

8.6. Physical Examinations

Physical examinations, including height (to be measured at the screening visit only) and weight, will be performed at screening, baseline, month 3, and end of treatment/early withdrawal visit. Any physical examination finding that is judged by the investigator as a clinically significant change (worsening) compared with a baseline value will be considered an adverse event, recorded on the CRF, and monitored as described in Section 7.1.2 of the study protocol. Shifts from baseline to each visit and last on study assessment will be summarized using patient counts.

Descriptive statistics for weight and height will be provided.

8.7. Vital Signs

Summary statistics for vital signs (pulse, systolic and diastolic blood pressure, body temperature, and respiratory rate) will be presented at baseline, each visit, and last on study assessment. Vital signs values and changes from baseline to each visit and last on study assessment will be summarized using descriptive statistics.

Summaries of potentially clinically significant abnormal values will include all postbaseline values (including scheduled, unscheduled, and early termination visits). The incidence of potentially clinically significant abnormal values will be summarized using descriptive statistics with the criteria specified in [Table 4](#).

[Table 4](#) specifies the criteria for identifying vital signs as potentially clinically significant abnormal values. Note that in order to qualify as potentially clinically significant abnormal, a value needs to meet both criteria below: ie, have a value beyond the criterion value and a change of at least the magnitude specified in the change relative to baseline column.

Table 4: Criteria for Potentially Clinically Significant Vital Signs

Vital Sign	Criterion value	Change relative to baseline
Pulse	≥120 bpm	Increase of ≥15 bpm
	≤50 bpm	Decrease of ≥15 bpm
Systolic blood pressure	≥180 mm Hg	Increase of ≥20 mm Hg
	≤90 mm Hg	Decrease of ≥20 mm Hg
Diastolic blood pressure	≥105 mm Hg	Increase of ≥15 mm Hg
	≤50 mm Hg	Decrease of ≥15 mm Hg
Respiratory rate	<10 breaths/min	
Body temperature	≥38.3°C	Change of ≥1.1°C

bpm=beats per minute

8.8. Electrocardiography

Twelve-lead ECGs will be performed in triplicate, with approximately 1-5 minutes between recordings. The average of the recorded measurements will be calculated for each visit.

Any ECG finding that is judged by the investigator as a potentially clinically significant change (worsening) compared with a baseline value will be considered an adverse event.

Shifts (normal and abnormal) from baseline to overall result interpretation and by visit will be summarized using patient counts. For overall result interpretation the worst postbaseline finding for the patient (the abnormal finding if there are both normal and abnormal findings) will be used in the summaries. Summary statistics for ECG variables and their corrected values will be presented. Actual values and changes from baseline to month 4, end of treatment visit, and last on study assessment will be summarized using descriptive statistics.

8.9. Electronic Columbia-Suicide Severity Rating Scale

The eC-SSRS will be used to assess the patient's suicidal ideation (severity and intensity) and behavior ([Posner et al 2011](#)). The eC-SSRS 'Baseline/Screening version' will be completed by the patient at visit 1 (screening), and the eC-SSRS 'Since Last Visit version' will be completed by the patient at months 1, 2, 3, 4, and 5, and at the end of treatment visit.

The results from the eC-SSRS will be listed.

8.10. Concomitant Medications or Therapies

Concomitant therapies and medications, including medications that are taken on an as needed basis and occasional therapies, will be monitored during the study. Details of prohibited medications may be found in Section 5.6 of the study protocol. All concomitant medications will be coded using the WHO Drug.

The incidence of concomitant therapies and medications will be summarized using descriptive statistics by therapeutic class category and preferred term. Patients are counted only once in each therapeutic class and only once in each preferred term category. Concomitant therapies and medications will include all medications up to the end of study as defined in the study protocol.

The subset of concomitant pain medication and medication or therapy for migraine/headache will be summarized by the following indication categories.

- migraine/headache preventive medication
- triptans and ergots for migraine/headache
- triptans and ergots for reasons other than migraine/headache
- butalbital for migraine/headache
- butalbital for reasons other than migraine/headache
- NSAIDs for migraine/headache
- NSAIDs for reasons other than migraine/headache
- opioids for migraine/headache

Statistical Analysis Plan

- opioids for reasons other than migraine/headache
- preventive medication for other reasons

9. TOLERABILITY VARIABLES AND ANALYSIS

Local tolerability findings will be listed and summarized descriptively.

10. PHARMACOKINETIC ANALYSIS

Pharmacokinetic plasma concentration results for fremanezumab will be tabulated descriptively at each planned sampling time point by treatment group and indication. In addition, the most appropriate population pharmacokinetic model may be developed, and covariates that may affect it will be tested for inclusion in the model. If performed, this analysis will be reported separately.

11. PHARMACOKINETIC/PHARMACODYNAMIC ANALYSIS

The pharmacokinetic/pharmacodynamic relationship may be estimated by compartmental techniques. The pharmacokinetic parameters will be based on IMP measurements. The pharmacodynamics analysis will be the efficacy response(s).

The pharmacokinetic/pharmacodynamic relationship may be estimated using the most appropriate model after comparing different candidate models for their quality of fit. Covariates that may affect the pharmacokinetic/pharmacodynamic relationship will be tested for inclusion in the model. If performed, this analysis will be reported separately.

